 - a. Blinded CGM (Guardian Link (3) Transmitter and Guardian Sensor (3)) will only be worn at baseline, 3 months, and 6 months (two weeks of sensors use). There will be N=140.

Cohort 2: MDI

The Study Period: After completion of the run-in period, subjects with MDI therapy (minimum of N=280) will be randomized and placed into one of 2 different arms during the study period:

- 1. The HCL Arm will use the MiniMed system (i.e., using Auto Mode) for 6 months during the study period. There will be N=140 for the HCL arm.
- 2. The Control Arm will be using their current insulin therapy (MDI).

The Multiple Daily Injection (MDI) subjects will remain on MDI therapy with subjects using their own insulin for 6 months during the study period. The Sponsor will not provide insulin. Blinded CGM (Guardian Link (3) Transmitter and Guardian Sensor (3)) will only be worn at baseline, 3 months and 6 months (two weeks of sensors use). There will be N=140.

MDI subjects who are currently using CGM, i.e. Dexcom or Medtronic Guardian Connect or who are currently using a SMBG alternative, i.e. Libre, will be allowed to enroll in the study and continue using their own device. There will be N=100

Cohort 3: SAP

The Study Period: After completion of the run-in period, subjects with SAP

[figure not shown]
CEP304 Clinical I	CEP304 Clinical Investigation Plan						
CEP304DOC	Revision	Н	Page 24 of 182	Medtronic			

therapy (minimum N=280) will be randomized and placed into one of 2 different arms during the study period. Sensor insertion placement will be according to User guide:

- 1. The HCL Arm will use the MiniMed system (i.e., using Auto Mode) for 6 months during the study period. There will be N=140 for the HCL arm.
- 2. The Control Arm will be using SAP therapy using the MiniMed System.
 - a. The Sensor Augmented Pump (SAP) subjects will use the MiniMed System (SAP without Low Management Suspend on Low, Low Management Suspend before low or Auto Mode) with Real Time CGM for the 6 month study period. There will be N=140.

The Continuation Period: All subjects above will enter the continuation period for 6 months using the MiniMed system with Auto Mode on.

CEP304 Clinical Investigation Plan CEP304DOC Revision H Page 25 of 182 Medtronic

[figure not shown]
CEP304 Clinical Investigation Plan CEP304DOC Revision Н Page 26 of 182 Medtronic

Age at time of screening:					

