17.2 Reporting of Adverse Events

The investigator or designee will record ALL adverse events while the Subject is enrolled in the clinical study. Each AE needs to be assessed for its device or procedure relatedness. A device related AE is associated with the use of the study/Medtronic device (e.g. infection of sensor site or infusion set occlusion resulting in DKA). A procedure related AE is associated with testing related to the study procedures specified in the CIP (e.g. IV insertion pain).

Examples include:

- Device related (ADE): insertion site infection
- Serious adverse device effect: cellulitis at device insertion site requiring hospitalization
- Procedure related AE: bruising at IV insertion site
- Not related to procedure or device: cold, flu, appendicitis

Subjects participating in the study have diabetes and are expected to experience hypoglycemia and or hyperglycemia. These normal events are not expected to be reported to sponsor on an AE eCRF as this is not considered an untoward event, but rather an expected occurrence. Any glycemic excursion that meets the protocol definition of Severe Hypoglycemia, Severe Hyperglycemia or DKA is considered an untoward event and a worsening from the subject's baseline and would be reported to sponsor on an AE eCRF.

Baseline medical conditions should only be reported to sponsor on an AE eCRF if there is a worsening from the subject's baseline. For example, a subject previously diagnosed with Asthma is hospitalized for severe asthma attack would be a reportable event.

Adverse events will be documented in the subject source file and reported to sponsor on an eCRF. The investigational center is responsible for documentation of adverse events including obtaining source documents related to the event, such as emergency medical technician/paramedic reports, hospital records (admission summary; lab results, test results, discharge summary) or device uploads to support the event. Source documents will be reviewed to determine if additional adverse events have occurred and require reporting.

Narratives gathered from completed questionnaires will not provide the basis of an adverse event report however could lead to discussions that result in the identification of a reportable AE.

CEP304 Clinical 1				
CEP304DOC	Revision	Н	Page 127 of 182	Medtronic

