Third: Based on their meetings, DMC will recommend a decision to the sponsor regarding the following:

- Whether or not enrollment should be halted.
- Whether or not the entire study will need to be stopped including for those subjects who have received study devices already.

Fourth: During Interim analysis, independent statistician will perform sample size re-estimation and report it to DMC. DMC will then provide a recommendation:

- Whether or not N of enrollment per Group should be increased
- Whether or not the entire study will need to be stopped for futility

General guidance for DMC's recommendations to sponsor should be based on the following:

In general, a DMC recommendation regarding study stoppage or resumption of enrollment should be made to the sponsor within 1 week of the DMC meeting where the determination is made. However, if more data is needed, the DMC may meet again to re-assess their decision within 2 weeks or when required data becomes available.

Review of events may require the following information. Final disposition may be delayed based on obtaining this information:

- Monitoring by sponsor at site
- Device return and failure analysis
- CareLink upload and review of CareLink reports
- Subject clarification to site regarding details about the event
- Source documents that support event: Paramedic records; ER records; Lab records; Hospital admission and discharge summary

The following factors should be carefully considered in the DMC's recommendation to sponsor:

- 1. Was the severe hypoglycemia or DKA related to the HCL algorithm, or was it related to a known insulin pump risk? For example, a question that may be considered in DKA would be whether the event was related to an infusion set issue or caused by the HCL algorithm.
- 2. Another important consideration would be if the severe hypoglycemia, severe hyperglycemia or DKA event was related to a device malfunction versus patient non-compliance. For example, if a software anomaly leading to an under-delivery of insulin is discovered versus the subject repeatedly ignoring alarms prompting the subject to take action.

CEP304 Clinical				
CEP304DOC	Revision	Н	Page 133 of 182	Medtronic

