- 3. Severe hypoglycemia, severe hyperglycemia or DKA caused directly by an infusion set issue when the study pump is functioning as intended would likely result in acceptance to proceed with the study versus severe hypoglycemia or DKA that are directly caused by the HCL algorithm or a device malfunction might stop study enrollment or entire study altogether.
- 4. It should be noted that the final determination of causality related to HCL System that is made by the DMC may include additional factors which the members consider to be clinically relevant and important.
- 5. The DMC may take into account the thresholds listed below for the number of subjects experiencing hypoglycemia requiring assistance from another person or DKA to identify when the number of subjects experiencing these events exceeds the number that would be anticipated for the study population over the duration of this study. These thresholds should be interpreted with caution due to potential differences in study populations and study design.
 - a. Rates taken from Type 1 exchange (Cengiz et. Al, and Weinstock et. Al), are higher than the clinical studies STAR 3, 530G adult in-home study (CEP266) and 530G Pediatric in-home study(CEP287).
 - b. Reasons for lower rates of severe hypoglycemia and DKA in the clinical studies mentioned could be related to several factors including but not limited to the exclusion of those with DKA or severe hypoglycemia, additional attention secondary to mandatory study visits, selection bias of motivated patients willing to perform study procedures and access to free study devices during the course of the study.
 - c. The CL outcome study (CEP304) will include several aspects noted above including the provision of free study devices during the course of the study. Therefore, the DMC should consider stopping study if rates of severe hypoglycemia and DKA are significantly worse (e.g. higher) in HCL arm than rates provided by clinical trials mentioned in Table 16.
 - d. Age consideration may also be factored in by the DMC. For example, severe hypoglycemia rates in those >25 years may be higher than those 25 years and below.
 - e. Should DKA and/or severe hypoglycemia occur early in the study, the DMC should consider that the higher event rate may not necessarily represent a significant safety concern.

CEP304 Clinical Investigation Plan

CEP304DOC Version H Page 134 of 182 **Medtronic**

Table 16. Hyperglycemia/Hypoglycemia / DKA Threshold

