19.1.6 Analysis of Endpoints

Primary Effectiveness Endpoints:

Test will be tested against the 0.025 (one-sided) significance level and both have to be met to claim success for the associated Cohort.

Group1 – Baseline A1C > 8%: Change in A1C (ΔA1C)

The initial univariate analysis for this endpoint will be an analysis of covariance at six months. If the computed F-statistic has a one-sided P<0.025 (can be computed from the two-sided F-statistic by taking the square root and comparing to a one-sided t-statistic), the null hypothesis will be rejected in favor of the alternative, Other supporting analysis including multivariable modeling may also be done to support this finding.

Group2 – Baseline A1C ≤ 8%: Time in Hypoglycemic Range

The initial univariate analysis for this endpoint will be an analysis of covariance F-test at six months. If the computed F-statistic has a one-sided P<0.025 (can be computed from the two-sided F-statistic by taking the square root and comparing to a one-sided t-statistic), the null hypothesis will be rejected in favor of the

CEP304 Clinical	Investigatio			
CEP304DOC	Revision	Н	Page 144 of 182	Medtronic

alternative. Other supporting analysis including multivariable modeling may also be done to support this finding.

CEP304 Clinical I				
CEP304DOC	Revision	Н	Page 145 of 182	Medtronic

[figure not shown]

CEP304 Clinical Inv	estigation	n Plar	1	
CEP304DOC	Revision	Н	Page 146 of 182	Medtronic

CEP304DOC	Revision	Н	Page 147 of 182	Medtronic
	_			•

CEP304 Clinical Investigation Plan CEP304DOC Revision H Page 148 of 182 Medtronic

[figure not shown]
CEP304 Clinical Investigation Plan CEP304DOC Revision H Page 149 of 182 Medtronic

CEP304 Clinical Investigation Plan CEP304DOC Revision H Page 150 of 182 Medtronic

CEP304 Clinical Inv					
CEP304DOC	Revision	Н	Page 151 of 182	Medtronic	

[figure not shown]
CEP304 Clinical Inv				
CEP304DOC	Revision	Н	Page 152 of 182	Medtronic

[figure not shown]

CEP304 Clinical Inv					
CEP304DOC	Revision	Н	Page 153 of 182	Medtronic	

CEP304DOC	Revision	Н	Page 154 of 182	Medtronic	
1					
-					

CEP304 Clinical 1				
CEP304DOC	Revision	Н	Page 156 of 182	Medtronic

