7.9 Evaluation of Objectives

Primary Safety Endpoint:

The primary safety endpoint is the event rate of severe hypoglycemia and DKA from both Groups (1 & 2) during the first 6 months of study period and second 6 months of continuation period. The descriptive summary statistics will be presented by number of event and event rate (100 patient years) for severe hypoglycemia and DKA **separately**.

Descriptive summary (i.e. not statistically powered) for severe hypoglycemia and DKA events rates will be performed between the HCL and control arms for each age group (< 15 years, 15-25 years, and > 25 years), as well as the overall event rates.

[figure not shown]
In order to achieve safety success, the following study success criteria must be met for the HCL Arm by the end of the study:

Table 1. Safety Success Criteria

Adverse Event	Reference	Reference Rate > 25 years old	Reference Rate 15-25 years old	Reference Rate <15 years old	Study Success Criteria
DKA events per 100 patient years	STAR 3 Bergenstal et. al	SAP arm: 0.68 Control arm: 0	SAP arm: 2.7 Control arm: 3.6	SAP arm: 2.2 Control arm: 0	
	530 G Adult inhome study CEP 266 (MDT on file)	1.27	3.4	N/A	≤4 events per 100 patient years with HCL arm
	530 G Pediatric inhome study CEP 287 (MDT on file)	N/A	N/A	0	
	Type 1 exchange Weinstock et. al	4.8	N/A	N/A	
	Type 1 exchange Cengiz et. al	N/A	9.9	9.9	

Revision 3.0

Page 22 of 34

Severe hypoglycemia per 100 patient years	STAR 3 Bergenstal et. al	SAP arm: 16.5 Control arm: 20.9	SAP arm: 5.4 Control arm: 3.9	SAP arm: 10.2 Control arm: 3.6	
	530 G Adult inhome study CEP 266 (MDT on file)	0.85	0	N/A	< 8 events per 100 patient
	530 G Pediatric inhome study CEP 287 (MDT on file)	N/A	N/A	1.42	years with HCL arm
	Type 1 exchange Weinstock et. al	11.8	N/A	N/A	
	Type 1 exchange Cengiz et. al	N/A	6.2	6.2	

Descriptive summary (i.e. not statistically powered) for severe hypoglycemia and DKA events rates will be performed between the HCL and control arms for each age group (< 15 years, 15-25 years, and > 25 years), as well as the overall event rates.

Severe hypoglycemia and DKA event rates were taken from the following

- 1. Richard Bergenstal et.al: Effectiveness of Sensor-Augmented Insulin-Pump Therapy in Type 1Diabetes.New England Journal of Medicine, 2010; 363:311-20
- 2. Weinstock et. al: Severe hypoglycemia and diabetic ketoacidosis in adults with type 1 diabetes: results from the T1D Exchange clinic registry. J Clin Endocrinol Metab. 2013 Aug;98(8):3411-9.

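### Infusion-set DKA is a between-arm effect of HCL only in the MDI cohort during the randomised period, yet the visible safety plan has no split by Cohort and the DMC guidance on such events is not aligned with the adverse-event rules

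*Protocol*

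**What the plan says.** **DMC guidance.** Protocol 18.2 lists factors for the DMC's recommendation. Item 1 asks, for DKA, "whether the event was related to an infusion set issue or caused by the HCL algorithm". Item 3 covers DKA, severe hyperglycemia and severe hypoglycemia. It says that an event "caused directly by an infusion set issue when the study pump is functioning as intended would likely result in acceptance to proceed", and contrasts this with events caused by the algorithm or a device malfunction. Item 4 adds that the final causality decision "may include additional factors which the members consider to be clinically relevant and important". Item 5c asks the DMC to consider stopping if HCL-arm rates are "significantly worse (e.g. higher) in HCL arm than rates provided by clinical trials mentioned in Table 16".

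**Adverse-event rules.** Protocol 17.2 gives "infusion set occlusion resulting in DKA" as an example of a device-related event. The worked example in 10.7.2, for severe hyperglycemia, scores a detached set, bent cannula or occlusion alarm as a causal relationship.

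**Control treatments.** In the protocol's study design, CSII controls use the study pump without CGM and SAP controls use it with CGM. MDI "subjects will remain on MDI therapy with subjects using their own insulin for 6 months during the study period". Visit 3 starts the pump for everyone except MDI controls, who start it at Visit 9.

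**Success rules.** Protocol 19.1.6 says of the two co-primary effectiveness tests that "both have to be met to claim success for the associated Cohort". For safety, SAP 7.9 says: "In order to achieve safety success, the following study success criteria must be met for the HCL Arm by the end of the study". The limits are 4 DKA events and 8 severe hypoglycemia events per 100 patient-years. Protocol 19.1.2 and SAP 7.9 plan descriptive rates for the HCL and control arms by three age groups and overall. SAP 7.10 summarises safety per arm.

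**The concern.** Treating infusion-set DKA as a known pump risk suits a comparison in which both arms wear a pump, because the risk is then common to both. In Cohort 2 it is not. A subject who moves from injections to HCL takes on the infusion set as part of the assigned treatment, and the MDI control does not. DKA from that source belongs to the treatment effect that the cohort was randomised to estimate.

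At stake is whether the trial can show an excess specific to subjects who come from injections. The guidance leans towards proceeding after such events, the stated DMC benchmark is external trials, and the planned end-of-study breakdown has no Cohort dimension. A reader of a positive Cohort 2 effectiveness result would then have no matching safety result from the same randomised comparison.

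**Working it through.** **1. Where the arms differ in infusion-set use during the 6-month study period**

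| Cohort | HCL arm | Control arm |
|---|---|---|
| 1 CSII | study pump | study pump |
| 2 MDI | study pump | injections until Visit 9 |
| 3 SAP | study pump | study pump |

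Only Cohort 2 is asymmetric, and only until Visit 9 (day 180). After that every subject is on the pump and no control arm remains.

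**2. The plan's own figure.** The visible text gives no derivation, power or error rate for the DKA limit of 4, so there is nothing to reproduce. The counts agree: 70 + 70 = 140 per arm, 140 + 140 = 280 per cohort, and 3 × 140 = 420 in HCL arms. The limit is printed with < in the protocol synopsis and ≤ in the SAP. This does not change any result below.

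**3. How far one cohort can differ before an overall limit reacts.** Take the plain reading that one rate is formed over all HCL subjects. Let m be the DKA rate in the MDI cohort's HCL arm and o the rate in the other two cohorts, per 100 patient-years. With equal arms and equal follow-up:

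pooled rate = (140m + 280o) / 420 = (m + 2o) / 3

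Setting this to 4 gives m = 12 − 2o. The length of follow-up cancels.

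Protocol 19.1.4 also places all children aged 2–6 in the HCL arm, with a study minimum of 120. If they count in the arm and, by assumption, none is in the MDI cohort, then m = (4 × 540 − 400o) / 140.

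| Assumed o | m at the limit, 420 subjects | m at the limit, 540 subjects |
|---|---|---|
| 0 | 12 | 15.4 |
| 1 | 10 | 12.6 |
| 2 | 8 | 9.7 |
| 3 | 6 | 6.9 |

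In the first case m is 1.5 to 3 times the limit. For severe hypoglycemia, with a limit of 8, the same algebra gives m = 24 − 2o.

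**4. Chance of meeting the limit, one illustration.** Assume true rates of m = 8 and o = 1, Poisson counts and 420 HCL subjects.

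- 6 months: 210 patient-years, limit 0.04 × 210 = 8.4, so at most 8 events. Expected 0.08 × 70 + 0.01 × 140 = 7.0. P(X ≤ 8) = 0.73.
- The same figure of 4 read on the MDI cohort's HCL arm alone: 70 patient-years, limit 2.8, at most 2 events, expected 5.6. P(X ≤ 2) = 0.08.
- 12 months: at most 16 events with 14 expected, probability 0.76. MDI alone: at most 5 with 11.2 expected, probability 0.03.

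The single-cohort rows show only how much the averaging matters. They are not a suggested criterion.

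**5. What a Cohort 2 comparison could show.** Each arm gives 140 × 0.5 = 70 patient-years. Rates of 4 and 1 per 100 patient-years would mean 2.8 and 0.7 expected events. An observed 3 versus 1 has a one-sided exact p of P(X ≥ 3 of 4) = 5/16 = 0.31. The exact 95% Poisson interval for 3 events is 0.619 to 8.767; divided by 0.70, that is 0.9 to 12.5 per 100 patient-years.

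**The case against.** The strongest reply is that the safeguards already count these events. Item 3 is soft guidance on whether to proceed and removes nothing from any count. Under 18.2 the DMC tracks the rates of DKA, all SAEs and device-related events regardless of cause. Item 5c applies to HCL-arm rates without excluding a cause, and item 4 leaves discretion. The end-of-study limits count DKA of every cause. The CEC reviews every DKA, and one DKA withdraws the subject in any arm. All of this stands.

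Four stronger readings are therefore not supported.

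- *Infusion-set DKA is discounted or set aside.* The documents exclude no such event. In an overall rate it is averaged with the other cohorts, which is different.
- *18.2 flatly contradicts 17.2.* One passage concerns the decision to continue, the other relatedness for reporting, and both attribute the event to the pump system. What needs reconciling is that 18.2 sets these events apart from device faults without saying how a device-related event should weigh where only one arm wears the device. Item 2 of 18.2 does not mention infusion sets.
- *Cohort 2 could be declared safe.* No passage provides a safety declaration by cohort. The per-Cohort rule concerns effectiveness only.
- *No comparison by arm is planned.* It is planned, by age group and overall. Only the Cohort split is not visible.

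Two further cautions hold. Pooling over cohorts is the natural reading of the HCL arm and the overall rates, but no sentence says so. Parts of protocol 19 and SAP 7 are not public, so a Cohort split may exist there. The interim review is per Cohort, although the function given for it in 18.2 is sample-size re-estimation and futility.

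The reply that a Cohort table would be too imprecise to help is half right. It would rarely be conclusive, but it would stop a large excess from being averaged away unseen.

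**Conclusion.** The point holds as a gap in reporting and in the coherence of the guidance. During the randomised 6 months, infusion-set DKA in Cohort 2 is a consequence of assignment to HCL. The visible plan offers no safety result that isolates it, although effectiveness is claimed at that level.

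The size depends on assumptions. With equal HCL arms, equal follow-up and one rate across cohorts, the MDI cohort's HCL arm could run at 6 to 12 DKA events per 100 patient-years before the limit of 4 was reached, for assumed rates of 3 down to 0 elsewhere. The ceiling is higher if the HCL-only young children are counted outside that cohort. The documents give no DKA rate by cohort, so this is a range of what could go unnoticed and not a forecast. Nothing here shows that an excess exists.

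**What to change.** 1. In protocol 18.2, reconcile items 1 and 3 with 17.2 and 10.7.2, so that the DMC knows how the guidance on infusion-set events applies where only one randomised arm uses a set.
2. For Cohort 2, show the DMC all-cause DKA and severe hypoglycemia by randomised arm for the study period, with the attributed cause as additional information.
3. In SAP 7.9 and 7.10, add a descriptive table of both rates by Cohort and arm, with event counts, patient-years and exact intervals, beside the overall rates. Separate the randomised period from the continuation period, because MDI controls start the pump at Visit 9. Say whether the limits apply to one HCL arm across cohorts and whether children aged 2–6 are included.

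This proposes no stopping rule and no new threshold. It uses data already collected and costs some wording and one table split. The drawback is imprecision: about 70 patient-years per arm in 6 months means a handful of events at most plausible rates, so the table should be labelled descriptive.

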19.1 Statistical Methods and Data Analysis

19.1.1 General Aspects of Analysis

All endpoints are hierarchically ordered and will be evaluated in the fixed sequence from primary endpoints to secondary endpoints. Unless the primary endpoints hypotheses are rejected, secondary endpoints will not be tested.

Effectiveness endpoints will be evaluated during the 6 month study period by individual Cohort (CSII, MDI or SAP), stratified by A1C;

Group 1: Baseline A1C > 8%

• Group 2: Baseline A1C ≤ 8%

The comparison of HCL **arm** vs. Control **arm** will be performed. For SG-based comparison between HCL vs Control analyses, two weeks of CGM data collected at 3 month visit and 6 month visits will be used.

CEP304 Clinical I				
CEP304DOC	Revision	Н	Page 137 of 182	Medtronic

